11.2 DISPOSITION OF PATIENTS

The total number of patients for each of the following categories will be presented in the CSR:

- Screened patients: patients who have signed the informed consent;
- Randomized patients: patients with a treatment kit number allocated and recorded in IRT database, and regardless of whether the treatment kit was used or not;
- The modified intent-to-treat (mITT) population (as defined in [Section 11.3.1.1](#) and analyzed as randomized);
- The safety population (ie, randomized and treated patients);
- The pharmacokinetic (PK) population (as defined in [Section 11.3.3](#));
- The randomization strata [HbA1c at visit 1 (<8%, ≥8%) and GLP-1 receptor agonist subtype (once/twice daily formulations, once weekly formulations) at screening assigned by IRT will be summarized. The discrepancy between the strata assigned by IRT and the information reported on electronic Case Report Form (e-CRF) will be listed for all randomized patients;
- Patients who have completed the 26-week randomized treatment period;
- Patients who have completed the whole study treatment period including 26-week extension period;
- Patients who discontinued the IMP during the 26-week randomized treatment period, and the reasons for treatment discontinuation.
- Patients who discontinued the IMP during the whole study treatment period, and the reasons for treatment discontinuation.

For all categories of patients except screened patients, percentages will be calculated using the number of randomized patients as denominator for each treatment group.

A list of patients prematurely discontinued from the treatment, along with reasons for discontinuation, will be provided.

Patients treated but not randomized, patients randomized but not treated and patients randomized but not treated as randomized will be identified and described in separate listings. Only the patients of the third category (randomized and not treated as randomized) will be part of efficacy and safety analyses.

For any patient randomized more than once, only the data associated with the first randomization will be used in any analysis population. The safety experience associated with any later randomization will be assessed separately.

The safety experience of patients treated and not randomized will be reported separately, and these patients will not be in the safety population.

11.3 ANALYSIS POPULATIONS

11.3.1 Efficacy populations

Efficacy analyses will be based on the treatment group allocated by the IRT according to the randomization schedule at randomization visit (as randomized), irrespective of the treatment actually received.

11.3.1.1 Modified intent-to-treat population

Efficacy analyses will be based on the mITT population, defined as all randomized patients who have both a baseline assessment and at least one post-baseline assessment of any primary or secondary efficacy variables, irrespective of compliance with the study protocol and procedures. Patients will be analyzed for efficacy analyses according to the treatment group to which they are randomized.

11.3.2 Safety population

Safety analyses will be based on the safety population, defined as all randomized patients who receive at least one dose of open-label IMP (regardless of the amount of treatment administered). Patients will be analyzed for safety analyses according to the treatment actually received.

In addition:

- Nonrandomized but treated patients will not be part of the safety population, but their safety data will be presented separately;
- Randomized patients for whom it is unclear whether they took the study medication will be included in the safety population as randomized;

- When a patient is exposed to both FRC and GLP-1 receptor agonist, the patient will be analyzed in the treatment group (FRC or GLP-1 receptor agonist) in which he/she was treated longer;
- Patients will be excluded from the safety population only if there is documented evidence (ie, all study dates recorded as no medication taken) that patients have not taken the study medication.

11.3.3 Pharmacokinetic population

For pharmacokinetic (PK) analyses, the PK population is defined as all randomized and treated patients who contribute with at least one valid plasma analysis of lixisenatide.

11.4 STATISTICAL METHODS

Continuous data will be summarized by treatment group using the number of observations available (N), mean, standard deviation (SD), minimum, median, and maximum.

Categorical data will be summarized by treatment group using count and percentage.

In general, descriptive statistics of quantitative efficacy and safety parameters (result and change from baseline) by scheduled visits will be provided on observed cases (OC), ie, inclusion of only patients having non-missing assessments at a specific visit.

11.4.1 Demographic and baseline characteristics

The baseline value is defined as the last available value before the first dose of open-label Investigational Medicinal Product (IMP). Derived parameters will be computed by the sponsor.

Demographic characteristics to be summarized are:

- Age (years) derived as: $(\text{Date of informed consent} - \text{Date of birth})/365.25$;
- Age categories (<50 , ≥ 50 to <65 , ≥ 65 to <75 , ≥ 75 years of age);
- Gender (Male, Female);
- Race;
- Ethnicity (Hispanic, Not Hispanic);
- HbA1c (%) at V1(Week -2);
- Baseline BMI (kg/m^2) derived as: $(\text{Weight in kg})/(\text{Height in meters})^2$;
- Baseline BMI level (<30 , ≥ 30 kg/m^2);
- Randomization strata of HbA1c (<8 , $\geq 8\%$) at screening visit 1 (V1, Week -2);
- Randomization strata of GLP-1 receptor agonist subtype (once/twice daily formulations, once weekly formulations) at screening;
- Country.

Disease history includes:

- Duration of diabetes (years) derived as: (Date of informed consent – Date of diagnosis of diabetes + 1)/365.25;
- Age at onset of diabetes (years) derived as: (Date of diagnosis of diabetes – Date of birth + 1)/365.25;
- Duration of GLP-1 receptor agonist treatment (years) derived as: (Date of informed consent – Date of first dose of GLP-1 receptor agonist + 1)/365.25;
- Percentage of patients with GLP-1 receptor agonist use by type [once/twice daily formulations (Victoza® or Byetta®), once weekly formulations (Bydureon®, Tanzeum®, or Trulicity®)] at screening;
- Daily dose of GLP-1 receptor agonist (Victoza® or Byetta®) at baseline, or weekly dose of GLP-1 receptor agonist (Bydureon®, Tanzeum®, or Trulicity®) at baseline;
- Percentage of patients who used pioglitazone at screening (data from e-CRF);
- Duration of metformin treatment (years) derived as: (Date of informed consent – Date of first dose of metformin + 1)/365.25;
- Daily dose of metformin (mg) at baseline;
- Daily dose of pioglitazone (mg) at baseline (if used);
- Percentage of patients who used SGLT2 inhibitor at screening (data from e-CRF);
- Daily dose of SGLT2 inhibitor (canagliflozin, empagliflozin or dapagliflozin) at baseline (if used);
- Categorized daily dose of metformin at baseline (<1500, ≥1500 to <2500, ≥2500 to <3000, ≥3000 mg);
- Baseline diabetic microvascular complications (Yes, No) (ie, diabetic retinopathy, diabetic sensory or motor neuropathy, diabetic autonomic neuropathy, and diabetic nephropathy);
- Baseline urine albumin/creatinine ratio categories (<30 mg/g [Normal], ≥30 to <300 mg/g [Microalbuminuria], and ≥300 mg/g [Macroalbuminuria]);
- Estimated Glomerular Filtration Rate (eGFR) at screening (mL/min) /1.73m²;
- eGFR categories at screening (<15 mL/min/1.73m² [End stage renal disease], ≥15 to <30 mL/min/1.73m² [Severe decrease in GFR], ≥30 to <60 mL/min/1.73m² [Moderate decrease in GFR], ≥60 to <90 mL/min/1.73m² [Mild decrease in GFR], and ≥90 mL/min/1.73m² [Normal]).

The baseline efficacy variables include:

- HbA1c;
- During standardized meal test:
 - 2-hour postprandial plasma glucose (PPG) and glucose excursion;
 - C-peptide under fasting (30 minutes prior to the meal test before IMP administration if IMP is injected before breakfast) and 2-hour postprandial conditions;

Note: 2-hour plasma glucose excursion= 2-hour post prandial plasma glucose value – plasma glucose value obtained 30 minutes prior to the start of meal and before IMP administration if IMP is injected before breakfast.

- 7-point (average and each time point) SMPG;
- Body weight;
- Fasting plasma glucose (by central laboratory).

Medical history and medical findings include:

- Medical or surgical history (including physical examination abnormalities);
- Medical history of cardiovascular and cerebrovascular events;
- Medical history of allergies;
- Subject family allergy history;
- Alcohol habits within the last 12 months;
- Smoking habits.

Medical and surgical history will be coded using the version of Medical Dictionary for Regulatory Activities (MedDRA) currently in effect at Sanofi at the time of database lock. Medical history of cardiovascular and cerebrovascular events and medical history of allergies will be summarized by searching for relevant “preferred term (PT)” identified by medical and coding teams.

No statistical test will be performed for the between-group difference on demographic and baseline characteristics (including medical history and baseline efficacy data).

Demographic and baseline disease characteristics, baseline efficacy variables and medical history and medical findings will be summarized with appropriate descriptive statistics. Pathologies associated with past medical or surgical history will be summarized by primary system organ class (SOC) and high level term (HLT). These summaries will be provided on randomized patients for each treatment group (and overall).

11.4.2 Prior and concomitant medications

All medications will be coded using the version of World Health Organization-Drug Dictionary (WHO-DD) currently in effect at Sanofi at the time of database lock.

Medications will be classified into the following three groups:

- Prior medications are those the patient took prior to the first injection of open-label IMP;
- Concomitant medications are those the patient continued or started on or after the first dose of open-label IMP up to 3 days after the last injection of daily IMP or 9 days after the last injection of weekly IMP);
- Post-treatment medications are those the patient continued or started on or after 4 days after the last injection of daily IMP or 10 days after the last injection of weekly IMP.

A given medication can be classified in several groups. Medications will be summarized according to the WHO-DD, considering the first digit of the ATC class (anatomic category) and the first three digits of the ATC class (therapeutic category). All ATC codes corresponding to a medication will be summarized, patients will be counted once in each ATC categories (anatomic or therapeutic) linked to the medication, therefore patients may be counted several time for the same medication.

Summaries of prior, concomitant and post-treatment medications will be presented on randomized patients for each treatment group (and overall for the summary of prior medications) using counts and percentages. No statistical test for the between-group difference will be performed.

11.4.3 Extent of study treatment exposure and compliance

The extent of study treatment exposure and compliance will be assessed and summarized by actual treatment received in the safety population.

11.4.3.1 Extent of investigational medicinal product exposure

The extent of study treatment exposure will be assessed by the duration of treatment exposure during the study.

The duration of treatment exposure will be the total number of days of administration of the open-label investigational medicinal product, regardless of unplanned intermittent discontinuations.

The duration of daily IMP exposure will be calculated as:

$(\text{Date of the last open-label IMP injection} - \text{Date of the first open-label IMP injection}) + 1.$

The duration of weekly IMP exposure will be calculated as:

$(\text{Date of the last open-label IMP injection} - \text{Date of the first open-label IMP injection}) + 7.$

The number (%) of patients randomized and exposed to the open-label IMP will be presented by specific time periods for each treatment group in the safety population. The time periods of interest are grouped as follows:

- 1 to 14 days;
- 15 to 28 days;
- 29 to 56 days;
- 57 to 84 days;
- 85 to 126 days;
- 127 to 168 days;
- 169 to 182 days;
- 183 to 210 days;

- 211 to 238 days;
- 239 to 294 days;
- 295 to 364 days
- >364 days.

Descriptive statistics of duration of treatment exposure (number, mean, SD, minimum, median, and maximum) and cumulative exposure in patient year will also be presented by treatment group in the safety population.

11.4.3.2 Compliance

Overall treatment compliance is defined as the actual number of days with IMP injection compared to the planned number of days with IMP injection during the open-label treatment period, up to treatment discontinuation. It is calculated according to the following formula:

For once/twice daily formulation

$$\text{Compliance rate (\%)} = \left[\frac{\text{Total number of days with IMP injection}}{\text{Planned number of days with IMP injection}} \right] \times 100 .$$

For once weekly formulations,

$$\text{Compliance rate (\%)} = \left[\frac{\text{Total number of weeks with IMP injection}}{\text{Planned number of weeks with IMP injection}} \right] \times 100$$

11.4.4 Analyses of efficacy endpoints

Efficacy analyses will be performed on the mITT population using efficacy assessment obtained during the study, including those obtained after IMP discontinuation or introduction of rescue therapy, unless otherwise specified.

For a patient to be included in a change from baseline analysis (endpoint – baseline) or a baseline adjusted analysis of an endpoint, the patient must have both a baseline and a post-baseline measurement for that endpoint.

11.4.4.1 Analysis of primary efficacy endpoint

See [Section 9.1.1](#).

Primary analysis

The statistical test will be two-sided tests at a nominal 5% significance level.

The primary efficacy endpoint (change in HbA1c from baseline to Week 26) will be analyzed using a mixed-effect model with repeated measures (MMRM) under the missing at random

framework. The MMRM model will include treatment group (FRC or GLP-1 receptor agonist), randomization strata of HbA1c (<8%, ≥8%) at V1 (Week -2), randomization strata of GLP-1 receptor agonist subtype (once/twice daily formulations, once weekly formulations) at screening, visit (Week 8, Week 12, Week 18, Week 22 and Week 26), treatment-by-visit interaction and world region as fixed effects, and baseline HbA1c value-by-visit interaction as the covariates. The adjusted mean change in HbA1c from baseline to Week 26 for each treatment group will be estimated in the framework of this model, as well as the between group difference and the 95% confidence interval (CI) for the adjusted mean.

The MMRM model will be implemented using Statistical analysis system (SAS®) (Version 9.4 or higher) MIXED procedure (PROC MIXED) with an unstructured correlation matrix to model the within-patient errors. Parameters will be estimated using the restricted maximum likelihood method with the Newton-Raphson algorithm. Denominator degree of freedom will be estimated using the Kenward-Roger approximation by fitting values from post-randomization scheduled visits in the 26-week randomized treatment period. This model will use only scheduled HbA1c measurements.

Sensitivity analyses

The following sensitivity analyses will be performed for the primary endpoint:

- The same MMRM model as described in the primary analysis will also be performed by including only the scheduled HbA1c measurements collected during the 26-week on-treatment period (see [Section 9.2](#)).
- A sensitivity analysis will also be conducted on the 26-week completers in mITT population (ie, all mITT patients who completed the 26-week open-label randomized treatment period and did not start any rescue therapy before the end of the 26 week randomized treatment period) using the observed Week 26 values and the same MMRM model as described above.
- To investigate the impact of rescue medication, the same MMRM model as described in the primary analysis will be performed by excluding the measurements after receiving the rescue medication.
- In order for patients with missing data to be adequately represented by the patients with data, a sensitivity analysis using multiple imputations with respect to jump to control under the MNAR assumption will be performed. In particular,
 - For patients in the GLP1-RA group who have no HbA1c values at Week 26, the missing data will be considered as missing at random. Missing HbA1c values in this situation will be imputed by the regression method using the observed data from GLP-1 RA group. The regression imputation model will include baseline HbA1c values and randomization strata.
 - For patients in the FRC group who have no HbA1c value at Week 26, the missing HbA1c values will be imputed using baseline HbA1c values, randomization strata and coefficients generated from the regression model in the GLP-1 RA group plus an error. The error term will be randomly drawn from normal distribution with mean zero and a standard deviation. The standard deviation of the normal distribution will be calculated

from pooled standard error of the regression model in the GLP-1 RA group and the standard error of the regression model in the FRC group. The regression model in the FRC group will be generated using the observed data from FRC group and will include baseline HbA1c values and randomization strata.

- Missing HbA1c values at Week 26 will be imputed 100 times to generate 100 data sets with complete HbA1c values at Week 26. The change from baseline to Week 26 will be derived from observed and imputed HbA1c values at this time point. The completed data sets will be analyzed using an Analysis of covariance (ANCOVA) model with treatment groups, randomization strata, and world region as factors and the baseline HbA1c value as a covariate. The results from the 100 analyses will be combined using SAS PROC MIANALYZE.

Assessment of treatment effect by subgroup

Descriptive analyses will be performed on the primary endpoint to summarize the treatment effects across subgroups defined by the following baseline or screening factors:

- Race;
- Ethnicity (Hispanic, Not Hispanic);
- Age group (<50, ≥50 to <65, ≥65 to <75, ≥75 years of age);
- Gender;
- Baseline BMI level (<30, ≥30 kg/m²);
- Baseline GLP-1 receptor agonist subtype (once/twice daily formulations, once weekly formulations);
- Baseline HbA1c (<8%, ≥8%);
- Pioglitazone use (Yes, No) at screening;
- World region;
- Country.

The treatment effects across the subgroups defined for each of these factors will be estimated for the change from baseline to Week 26 in HbA1c in the mITT population, and using the MMRM approach with treatment group (FRC or GLP-1 receptor agonist), randomization strata of HbA1c (<8%, ≥8%) at V1 (Week -2), randomization strata of GLP-1 receptor agonist subtype (once/twice daily formulations, once weekly formulations) at screening visit, subgroup factor, treatment-by-visit, treatment-by-subgroup factor, visit-by-subgroup factor, treatment-by-visit-by-subgroup factor, and world region as fixed effects, and using the baseline HbA1c value-by-visit interaction as a covariate. The adjusted estimates of treatment mean differences (FRC versus GLP-1 receptor agonist) with standard errors and 95% CIs will be provided as appropriate across the subgroups.

In case that the subgroup factor is identical or similar to a randomization strata factor (eg, baseline HbA1c category and GLP-1 RA category), only the subgroup factor will be included in the model in order to avoid collinearity issue in the analysis.

In case that the subgroup factor is country, the world region will not be included in the model.

A similar MMRM model will also be used to estimate the within-group treatment effect for the change from baseline to Week 26 in HbA1c for the following subgroups:

- Anti-lixisenatide antibody status (positive, negative) at the end of 26-week treatment;
- Anti-insulin glargine antibody status (positive, negative) at the end of 26-week treatment;
- Anti-lixisenatide antibody concentration at the end of 26-week treatment: <lower limit of quantification (LLOQ), \geq LLOQ to 100 nmol/L, >100 nmol/L.

The adjusted means for each treatment group will be provided across the subgroups as appropriate, as well as the associated standard errors and 95% confidence intervals.

The change of HbA1c from baseline over time by visit will be evaluated by descriptive statistics (mean, SD, median and ranges) by treatment for the 26-week randomized treatment period and for FRC group for the whole study period including the extension period.

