2.4.4 Analyses of efficacy endpoints

Efficacy analyses will be performed on the mITT population using efficacy assessment collected during the study, including those obtained after IMP discontinuation or introduction of rescue therapy, unless otherwise specified.

For a patient to be included in a change from baseline analysis (endpoint – baseline) or a baseline adjusted analysis of an endpoint, the patient must have both a baseline and a post-baseline measure for that endpoint.

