2.4.4.1 Analysis of primary efficacy endpoint(s)

The statistical test will be 2-sided tests at a nominal 5% significance level.

Primary analysis

The primary efficacy endpoint (change in HbA_{1c} from baseline to Week 26) will be analyzed using a mixed-effect model with repeated measures (MMRM) under the missing at random framework. The MMRM model will include treatment group (FRC or GLP-1 receptor agonist), randomization strata of HbA_{1c} (<8%, ≥8%) at V1 (week -2), randomization strata of GLP-1 receptor agonist subtype (QD/BID formulations, QW formulations) at screening, visit (week 8, week 12, week 18, Week 22 and Week 26), treatment-by-visit interaction and world region as fixed effects, and baseline HbA_{1c} value-by-visit interaction as the covariates. The adjusted mean change in HbA_{1c} from baseline to Week 26 for each treatment group will be estimated in the framework of this model, as well as the between group difference in LS means and the corresponding 95% CI.

The MMRM model will be implemented using SAS® (Version 9.4 or higher) MIXED procedure (PROC MIXED) with an unstructured correlation matrix to model the within-patient errors. Parameters will be estimated using the restricted maximum likelihood method with the Newton-Raphson algorithm. Denominator degree of freedom will be estimated using the Kenward-Roger approximation by fitting values from post-randomization scheduled visits in the 26-week randomized treatment period. This model will use only scheduled HbA_{1c} measurements.

Primary analysis will be performed using the mITT population and including all scheduled HbA_{1c} measurements collected during the study, including those obtained after IMP discontinuation or introduction of rescue therapy.

Sensitivity analyses

The following sensitivity analyses will be performed for the primary endpoint:

- The same MMRM model as described in the primary analysis will also be performed by including only the scheduled HbA_{1c} measurements collected during the 26-week on-treatment period (see [Section 2.1.3](#)).
- A sensitivity analysis will also be conducted on the 26-week completers in mITT population (ie, all mITT patients who completed the 26-week open-label randomized treatment period and did not start any rescue therapy before the end of the 26 week randomized treatment period) using the observed Week 26 values and the same MMRM model as described above.

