- Race (American Indian or Alaska Native, Asian/Oriental, Black, Native Hawaiian or Other Pacific Islander, White, Other) (any category with less than 5 patients may be combined with another category as appropriate);
- Ethnicity (Hispanic or Latino, Not Hispanic or Latino);
- Age group (<50, ≥50 to <65, ≥65 to <75, ≥75 years of age) (any category with less than 5 patients may be combined with another category as appropriate);
- Gender;
- Baseline BMI level (<30, ≥30 kg/m²);
- GLP-1 receptor agonist subtype (QD/BID formulations, QW formulations) at screening
- Baseline HbA_{1c} (<8%, ≥8%);
- Pioglitazone use (Yes, No) at screening;
- SGLT2 inhibitor use (Yes, No) at screening (if each category contains sufficient number of patients);
- World region.

- Country

The treatment effects across the subgroups defined for each of these factors will be estimated for the change from baseline to Week 26 in HbA_{1c} in the mITT population, and using the MMRM approach with treatment group (FRC or GLP-1 receptor agonist), randomization strata of HbA_{1c} (<8%, ≥8%) at V1 (week -2), randomization strata of GLP-1 receptor agonist subtype (QD/BID formulations, QW formulations) at screening visit, subgroup factor, treatment-by-visit, treatment-by-subgroup factor, visit-by-subgroup factor, treatment-by-visit-by-subgroup factor, and world region as fixed effects, and using the baseline HbA_{1c} value-by-visit interaction as a covariate. The adjusted estimates of treatment mean differences (FRC versus GLP-1 receptor agonist) with standard errors and 95% CIs will be provided as appropriate across the subgroups.

In case that the subgroup factor is identical or similar to a randomization strata factor (eg, baseline HbA_{1c} category and GLP-1 RA category), only the subgroup factor will be included in the model in order to avoid collinearity issue in the analysis. In case that the subgroup factor is country, the world region will not be included in the model.

A similar MMRM model will also be used to estimate the within-group treatment effect for the change from baseline to Week 26 in HbA_{1c} for the following subgroups:

- Anti-lixisenatide antibody status (positive, negative) at the end of 26-week treatment;
- Anti-insulin glargine antibody status (positive, negative) at the end of 26-week treatment;
- Anti-lixisenatide antibody concentration at the end of 26-week treatment: <lower limit of quantification (LLOQ), ≥ LLOQ to 100 nmol/L, > 100 nmol/L.

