If the antibody measurement is not available at Week 26, the LOCF procedure will be used by taking the last available post-baseline antibody measurement as the value at Week 26.

The adjusted means for each treatment group will be provided across the subgroups as appropriate, as well as the associated standard errors and 95% confidence intervals.

Summary statistics at scheduled visits

Summary statistics (for screening value, baseline value, observed values, and observed changes from baseline) at scheduled visits (using OC) will be provided for each treatment group. The summary will include the number of observations, mean, SD, SE, minimum, median, and maximum. Graphical presentations will also be used to examine trends over time using mean values (±SE) and mean changes from baseline (±SE) at each of the scheduled visits (using OC). These analyses will be performed using efficacy assessments obtained during the 26-week randomized treatment period, including those obtained after IMP discontinuation or introduction of rescue therapy.

- Similar presentations will be provided for patients who have completed the 26-week treatment period. In addition, summary statistics tables will be presented using HbA_{1c} assessments obtained during the 26-week on-treatment period (see [Section 2.1.3](#)).

- Similar summary statistics and graphical presentations will also be provided for FRC group for the whole study period including the extension period.

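### The antibody-subgroup analysis of HbA1c includes values after FRC was stopped or rescue insulin added, so it does not isolate on-drug effect and may be distorted in either direction

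*Protocol*

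**What the plan says.** Protocol 11.4.4.1 and SAP 2.4.4.1 both plan an estimate of HbA1c change at Week 26 by anti-lixisenatide status, by anti-insulin glargine status, and by three bands of anti-lixisenatide concentration. All three are classified at the end of the 26-week treatment. The Protocol's description of the method is "A similar MMRM model will also be used to estimate the within-group treatment effect for the change from baseline to Week 26 in HbA1c", and the SAP's is the same: "A similar MMRM model will also be used to estimate the within-group treatment effect". The SAP alone adds a rule for missing antibody values: "If the antibody measurement is not available at Week 26, the LOCF procedure will be used by taking the last available post-baseline antibody measurement".

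Neither document names the HbA1c values that enter this model. The general rules are:

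- Protocol 11.4.4: all efficacy assessments count, "including those obtained after IMP discontinuation or introduction of rescue therapy, unless otherwise specified".
- SAP 2.4.4: "Efficacy analyses will be performed on the mITT population using efficacy assessment collected during the study, including those obtained after IMP discontinuation".
- SAP 2.4.4.1, for the primary MMRM that the antibody model resembles: "including all scheduled HbA_{1c} measurements collected during the study, including those obtained after IMP discontinuation or introduction of rescue therapy".

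Restricted data sets do appear in Protocol 11.4.4.1, but as sensitivity analyses of the overall between-arm comparison. One runs the MMRM "including only the scheduled HbA1c measurements collected during the 26-week on-treatment period". Another runs it "excluding the measurements after receiving the rescue medication". Neither is extended to the antibody subgroups.

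**The concern.** The natural use of this analysis is to see whether antibodies weaken FRC while patients are taking it. The model's HbA1c values answer a broader question. Patients who stop FRC stay in follow-up (Protocol 10.3.4), so their later HbA1c is measured off drug. Rescue in the FRC arm is rapid-acting insulin, considered after a repeated HbA1c above 8% (Protocol 8.2.3). It is therefore triggered by the outcome itself and then changes it.

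The all-data rule was adopted for a different purpose. SAP 1.5, Table 1, explains it by health-authority concern about the true response at the primary endpoint, which suits the comparison of the two arms. Elsewhere the SAP keeps antibody questions on treatment:

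- Hypoglycemia by antibody status uses the on-treatment period (SAP 2.4.5.1).
- Adverse events by antibody status are treatment-emergent events (SAP 2.4.5.2).
- Antibody variables have their own on-treatment window, ending 28 days after the last injection (SAP 2.1.4.8).

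In the available text this is the only analysis that links antibodies to HbA1c. If off-drug and post-rescue values drive it, neither a reassuring nor an alarming result could be read as an antibody effect.

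**Working it through.** **1. Which data set applies.** The antibody model states none. The default in both documents includes values after discontinuation and rescue unless something else is specified. Nothing else is specified for this model. On-treatment repeats are stated for the overall primary comparison, the by-visit HbA1c summaries (SAP 2.4.4.1), the secondary endpoints (SAP 2.4.4.2) and other endpoints (Protocol 11.4.5, SAP 2.4.4.4), but not here.

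**2. The plan's own figure.** Protocol 11.1 assumes a difference of 0.4, SD 1.1, two-sided 5% level, 90% power and 20% drop-out, with dropped FRC patients responding as control. The diluted difference is 0.8 × 0.4 = 0.32. That requires 249 per group by the normal approximation and 250 by the exact t calculation (power 90.1%), which reproduces the stated 250. The check has one use here: the plan itself assumes that patients off FRC dilute an effect by a fifth. No sample size or power is stated for the antibody subgroups.

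**3. Discontinuation only.** Let E be the on-drug benefit in antibody-negative patients relative to patients off drug, L the on-drug loss in positives, and fp and fn the shares of positives and negatives off drug at Week 26. The all-data gap is (1 − fn) × E − (1 − fp) × (E − L). E = 0.4 is borrowed from the planning difference; L, fp and fn are assumptions.

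| True loss L | fp | fn | All-data gap |
|---|---|---|---|
| 0.40 | 10% | 10% | 0.36 − 0 = 0.36 |
| 0.40 | 20% | 20% | 0.32 − 0 = 0.32 |
| 0 | 30% | 10% | 0.36 − 0.28 = 0.08 |
| 0 | 10% | 20% | 0.32 − 0.36 = −0.04 |

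Equal discontinuation dilutes a loss. Unequal discontinuation creates a gap of (fp − fn) × E where none exists.

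**4. Rescue only.** If rescue lowers HbA1c by r in shares gp of positives and gn of negatives, the gap is L − (gp − gn) × r. With L = 0.40, gp = 10%, gn = 5% and r = 0.5 to 1.0, it is 0.375 to 0.35. With gp = gn it stays at 0.40.

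**5. Both together, by simulation.** This is an FRC arm with the five scheduled HbA1c visits. All inputs are assumed: half the patients antibody-positive, on-drug change about −1.0 in negatives, return to baseline off drug, and rescue triggered by HbA1c above 8%. With a true loss of about 0.40, rescue reached about 25% of positives and 17% of negatives.

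| Scenario | Rescue effect | All-data gap | On-treatment gap under MAR |
|---|---|---|---|
| True loss about 0.40, no discontinuation | 0.5 to 1.0 | 0.36 to 0.33 | 0.40 to 0.41 |
| True loss about 0.40, 20% off drug in both groups | 0.5 to 1.0 | 0.28 to 0.25 | 0.40 to 0.42 |
| True loss about 0.30, 30% v 10% off drug | 0 to 1.0 | 0.40 to 0.35 | 0.29 to 0.31 |
| No true loss, 30% v 10% off drug | 0 to 1.0 | 0.20 to 0.22 | 0.00 to 0.01 |

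The false loss in the last row exceeds the 0.08 of step 3 because the benefit given up on stopping is larger: (0.30 − 0.10) × 1.0 = 0.20. The on-treatment estimates recover the true value partly by construction, because stopping was simulated as random within antibody group and rescue depended only on observed HbA1c.

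**The case against.** The strongest reply is that a subgroup analysis of the primary endpoint may properly follow the primary data rule. The on-treatment analysis estimates a different quantity and does not correct an error. The stated objective concerns the development of antibodies, listed under other objectives, not their effect on efficacy. The subgroup section is introduced as descriptive, with no test or power claim. This stands, and it limits the weight of the point. It is a reason to report both versions rather than replace one.

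Three stronger readings are tempting, and the documents do not support them.

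- A reader might infer that the analysis is biased toward finding no antibody effect. That needs similar discontinuation in both groups, or rescue concentrated in positives. Take on-drug changes of −1.0 in negatives and −0.7 in positives, and −0.6 off drug. With 10% of negatives and 30% of positives off drug, the means are −0.96 and −0.67. The gap is 0.29 against a true 0.30, so almost nothing is hidden.
- A reader might infer that about half of a real loss disappears. With those same changes and 20% off drug in both groups, the gap is 0.92 − 0.68 = 0.24. Getting to 0.14 requires rescue in 10% of positives and no negatives, each gaining a full 1.0 point. Equal rescue cancels and returns 0.24.
- A reader might infer that a patient who stops early is necessarily classified on an early antibody value. The flow chart schedules an antibody sample at V28, and patients off drug are followed under study procedures, so a later sample may exist. Carrying forward applies only if it does not. Whether the 28-day antibody window excludes that sample is not stated.

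Also fair: SAP Appendix C, which summarizes the analyses, is not in the available text, so an on-treatment antibody table there cannot be excluded.

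**Conclusion.** The point holds as a limit on interpretation. By the default rule in both documents, the antibody-subgroup MMRM mixes on-drug, off-drug and post-rescue HbA1c, and no on-treatment counterpart is stated in the available text. The result may be distorted in either direction. Under the assumptions above, a true loss of 0.40 shows as about 0.36 to 0.25, a shrinkage of roughly 10% to 40%. Excess discontinuation in antibody-positive patients produces a false loss of about 0.08 with E = 0.4, and about 0.20 if stopping forfeits a benefit of 1.0. Discontinuation and rescue rates by antibody status, the size of any antibody loss and the rescue effect are not in the documents, so these figures show possible size, not expected bias. The primary comparison and the sample size are unaffected.

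**What to change.** In Protocol 11.4.4.1 and SAP 2.4.4.1:

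- Also run the antibody status and concentration MMRMs on HbA1c from the 26-week on-treatment period already defined in Protocol 9.2.1.1 and SAP 2.1.3, which ends at rescue. Report them beside the all-data version.
- State that the models are fitted in the FRC arm only. Antibodies are measured only there (Protocol 9.2.2.6), yet the text promises adjusted means for each treatment group.
- Show discontinuation counts, rescue counts and FRC dose by antibody status next to the estimates.

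The cost is some wording and one further run on a data set already needed for the first sensitivity analysis; no new data are collected. There will be fewer Week 26 values, so slightly wider confidence intervals, and the on-treatment estimate relies on missing at random after discontinuation or rescue. FRC is titrated to a fasting glucose target, so a loss offset by a higher dose could be missed in both versions; the dose table is there to show it. The analysis remains descriptive.
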